12.5 Final analysis plan

The research study will be explained in lay terms to each potential research participant. The potential participant will sign an informed consent form before undergoing any study procedures. Once the informed consent has been signed, the participant is considered enrolled in the study and will be assigned a unique participant number. Each enrolled subject becomes part of the longitudinal study.

AIM 1: We will perform intergroup and intragroup baseline analysis at study entry, longitudinal analysis, and supportive and exploratory analysis with the expertise of our statisticians Drs. [name] and [name]. To describe the clinical profile for each disease entity, separate analysis will be performed at baseline for participants in the newly diagnosed cohort and the previously

diagnosed (ongoing cohort). Summary statistics, grouped by adults or children, will be calculated for the demographic and the outcome variables. Differences in these phenotypic variables between EoE, EG, and EC will be tested using ANOVA or chi square tests. To evaluate the correlation of peak eosinophils with COMs (e.g. PROs, EREFS, QoL metrics), multivariate regression analysis will be conducted separately for each COM, with the COM serving as the dependent variable and peak eosinophil counts as the independent variable. Covariates in the model will include, but are not limited to, sex, age group, atopic disease, race, disease duration, and medication usage. To assess the difference in the extent of this correlation between cohorts or age groups, an interaction term of peak eosinophil counts by the selected categorical variable will be introduced to and tested under the above model. Similarly, PROs will be correlated with the other endoscopy (EREFs, Lanza score, UCCIS) and histology (biopsy evaluation forms) measures using the same approach. The normality assumptions will be evaluated, and transformations will be used (e.g. square root, log, rank) as appropriate. The correlation analyses discussed above will be conducted separately for EoE, EG, and EC.

Longitudinal analysis will determine whether changes in COMs correlate with changes in peak eosinophil counts over time. To minimize the confounding effect of the change in therapies and in accompanying medical condition over time, the changes (or percent changes, as appropriate) at the clinic visit one year from enrollment will serve as the primary endpoint; therefore, patients will be enrolled in the longitudinal study for a minimum of one year. The treatment that participants received over this period will be determined and used to classify participants into treatment group. Multivariate regression analysis will be conducted separately for each COM with change in peak eosinophil count as the independent variable and the change in COM as the dependent variable. Model covariates will be the same as above; similar analysis of endoscopic and histological scores will be performed. As a supportive and exploratory analysis, the change in COMs will be compared between treatment groups while adjusting for imbalanced demographic variables. Should there be significant differences among treatment groups, the change in peak eosinophil count or histological variables will be introduced into the model to see whether the change in COMs is mediated through the change in peak eosinophil counts or the histological condition. Change in the significance of the coefficient for the group difference is in support of the mediator effect. In addition, a linear or non-linear mixed effects model, as appropriate, will be fit to the serial data of each outcome to describe the course of the disease. The normality assumptions will be evaluated, and transformations will be used (e.g. square root, log, rank) as appropriate. These analyses will be conducted separately for each of the three diseases (EoE, EG, EC).

AIM 2: Data analysis and statistical methods for EG and EC will be accomplished as previously reported for EoE^{26, 36}. In brief, individual array quality analyses, normalization, referencing, detection of differences at the exon level, and hierarchical and other clustering approaches are carried out using BioConductor, R, and GeneSpring version v7.3.1 (Agilent, Santa Clara, CA) software as detailed previously²⁶. To determine whether GOIs are also associated with tissue eosinophilia and COMs, we will use either Pearson or Spearman correlations for quantitative variables depending on the variable's distributional properties. Dichotomous outcomes t-tests or Mann-Whitney U will be used for comparisons. To determine the appropriate number of individuals (power), we used MD Anderson's Sample Size for Microarray Experiments. Assuming 30,000 genes and that some genes analyzed will not reach minimal expression levels, a sample size of 20 per group will yield 80% power to detect at least 2-fold differences with no more than 10 false positives. Given the exploratory nature of this Aim, we feel that this sample size appropriately balances statistical power with the currently available resources. Of note, depending upon the findings, results will be validated with qPCR and replication could be performed using additional resources available to CEGIR.

13 Quality Control and Quality Assurance

Training of observational study staff will be conducted by representatives of the DMCC and NIAID prior to beginning recruitment. All staff members will be required to complete certification and quality control in all applicable procedures as outlined in the MOO. The site principal investigators and coordinator(s) will be responsible for ensuring that all procedures are performed according to the protocol. Periodic reviews of procedures will be conducted by the coordinator or other trained personnel according to an individual schedule for each staff member, which is based on the activities he/she is responsible for conducting. Details of the quality control plan, including certifications and quality control of study procedures, are provided in the MOO.

14 Ethics/Protection of Human Subjects

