8.4 Follow-up (Phase 2)

In Phase 2 of this study, subjects enrolled in Phase 1 will continue to be followed and assessed at each of the following time points: 1.) annually, 2.) at the time of any change in SOC treatment and 3.) at the time of any endoscopic procedure (up to 4 endoscopies in one year). In scenarios 1, or 2, only PRO and QoL COMs will be completed and in scenario 3, all COMs and histological analysis will be analyzed. All patients will be undergoing SOC treatment during this time; SOC treatment will be the choice of the attending physician and may include systemic or topical steroids, diet, or immunosuppression. This is not an interventional study and thus *treatment will be monitored, but not prescribed* as a part of this protocol. We have taken this approach for several reasons including the capture of “real world” data such that study findings are broadly applicable to the EoE, EG, and EC populations at large, to allow entry of the largest cohort of subjects independent of therapeutic intervention, and to better understand patient adherence to a prescribed therapeutic regimen as it relates to disease course.

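### Treatment groups are defined by treatment received during the outcome year, so equal treatments can look different in the supportive comparison of COM change

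*Protocol*

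**What the plan says.** Protocol section 12.5 sets the outcome window: "the changes (or percent changes, as appropriate) at the clinic visit one year from enrollment will serve as the primary endpoint". It gives its reason: "To minimize the confounding effect of the change in therapies and in accompanying medical condition over time". The grouping rule follows directly: "The treatment that participants received over this period will be determined and used to classify participants into treatment group". Outcome and exposure therefore cover the same year.

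The groups are then used twice. First: "As a supportive and exploratory analysis, the change in COMs will be compared between treatment groups while adjusting for imbalanced demographic variables". Second, a significant result opens a mediation analysis: "Should there be significant differences among treatment groups, the change in peak eosinophil count or histological variables will be introduced into the model". If the significance of the group coefficient then changes, the plan counts this in favour of mediation.

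Section 8.4 describes how treatment is decided: "SOC treatment will be the choice of the attending physician and may include systemic or topical steroids, diet, or immunosuppression". It lists as an assessment point "at the time of any change in SOC treatment", so changes within the year are expected. No section says how a participant with more than one treatment in the year is coded, and none offers a classification fixed at the start of the year.

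**The concern.** A participant's group under this rule is known only once the year is over. If physicians change treatment because of how the patient is doing, those who stay on one treatment are selected on their course, and so are those who change. Group membership then carries information about the outcome.

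This differs from confounding by the initial choice of treatment. It would arise even if starting treatment were random, and adjustment for demographic or other baseline variables cannot remove selection on what happens after baseline. Section 12.5 recognises change in therapies as a confounder, but its remedy, the one-year change, leaves the switching inside the exposure definition.

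At stake are the supportive comparison and the mediation step. If switchers fared worse in both symptoms and histology, adding change in peak eosinophils would tend to shrink a spurious group coefficient, and the plan would read that as support for mediation. One artefact could thus produce both an apparent treatment difference and an apparent mediator.

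**Working it through.** **The plan's own figures.** Section 12.4 gives none for this comparison. Its Table 3 concerns correlations and reproduces: tanh[(2.576 + 0.842)/√(n − 3)] gives 0.275, 0.196 and 0.139 for n = 150, 300 and 600, against 0.27, 0.20 and 0.14 printed (two-sided alpha 0.01, 80% power, no covariates). It does not bear on the bias.

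**Inputs.** From the Protocol: 150 EC, 300 EG and 600 EoE participants, used as total n. Assumed, because the Protocol gives no switch rates, reasons for switching or SDs:
- two identical treatments A and B, half the sample starting on each, and no effect of treatment or of switching;
- one-year change y = 0.6m + 0.8e, where m is mid-year change, m and e are standard normal, and higher is worse (SD of y is 1);
- probability of switching 1/[1 + exp(−(b + 1.5m))], with b set to give the switch rate;
- two-sided test at 0.05, 1,000 simulated studies per setting.

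**Step 1: the gap.** The simulated mean of switchers minus non-switchers, g, is 0.72 to 0.73 SD at 10% switching, 0.67 to 0.68 at 20% and 0.65 to 0.66 at 30%.

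**Step 2: from gap to group difference.** With no treatment effect each starting arm has mean 0. If a fraction s switches, non-switchers have mean −s·g and switchers (1 − s)·g.
- A only versus any B, 20% switching each way: A only is −0.2 × 0.68 = −0.136. Any B is all B starters (half the sample, mean 0) plus A-to-B switchers (0.1 of the sample, mean 0.8 × 0.68 = 0.544), so 0.1 × 0.544/0.6 = 0.091. Difference 0.23. Last treatment with 20% A to B and none back gives the same two groups in effect, and 0.23 again.
- Last treatment, 30% A to B and 10% B to A: ended on A, [0.35 × (−0.195) + 0.05 × 0.657]/0.40 = −0.089; ended on B, [0.45 × (−0.073) + 0.15 × 0.455]/0.60 = 0.059. Difference 0.15.
- Non-switchers only, same rates: −0.073 + 0.195 = 0.12.
- Equal switching both ways, last treatment or non-switchers only: 0 by symmetry.

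**Step 3: simulated results.**

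| Classification and switching | Spurious difference (SD) | False positives, n = 150 / 300 / 600 |
|---|---|---|
| A only vs any B, 20% each way | 0.22–0.23 | 27% / 51% / 78% |
| Last treatment, 20% A to B only | 0.22–0.23 | 26% / 49% / 79% |
| Last treatment, 30% vs 10% | 0.14–0.15 | 16% / 24% / 43% |
| Non-switchers only, 30% vs 10% | 0.12–0.13 | 10% / 16% / 30% |
| A only, B only, switched; 10% | about 0.7 for switchers | 66% / 93% / 100% |
| Last treatment or non-switchers, equal switching | none | 3% to 6% |
| Three groups, switching unrelated to response | none expected | 4% to 6% |
| Treatment at start of period | within 0.01 of 0 | 4.0% to 6.3% |

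At 40% against 10% switching, the last-treatment and non-switcher rules gave 0.18 to 0.20 SD; A only versus any B gave 0.36. The row with switching unrelated to response isolates the cause: the error comes from response-driven switching combined with the grouping rule.

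**The case against.** The strongest reply is that little depends on this comparison. Section 12.5 labels it supportive and exploratory. The main longitudinal regression, of COM change on change in peak eosinophils, does not use these groups and has only a medication-usage covariate. This stands and limits the reach to the comparison and its mediation step.

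It can also be said that coding patients with several treatments belongs in a statistical analysis plan. That is true of the coding. The exposure window, however, is fixed in the Protocol, and most codings of it are open to the bias if switching is uneven or switchers are kept apart.

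A reader might infer that escalated treatment will look harmful and that response to therapy will be answered in the wrong direction. The documents do not support that. They give no reason for treatment changes, and stepping down after improvement would push the bias the other way. The secondary objective (section 3.2) and its endpoint (section 4.2.2) ask how COMs change over time and during standard care, not which treatment is better.

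A reader might also derive a gap of 0.5 to 1.2 SD and set it against the 0.35 in section 12.4. The arithmetic is sound: if everyone below the p-th percentile of early change switches, the gap is ρφ(z_p)/[p(1 − p)], which for p = 0.2 to 0.4 is 0.48–0.52, 0.80–0.87 and 1.13–1.22 SD at ρ = 0.3, 0.5 and 0.7. But it assumes a hard threshold and contrasts switchers with non-switchers, a contrast the plan does not name. The 0.35 is a detectable size for differences among disease groups, with no unit stated, and is no benchmark here.

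**Conclusion.** The point holds as a possible bias in a supportive analysis. The rule as written lets group membership depend on the outcome, and the demographic adjustment cannot correct that. Whether it does so in practice depends on treatment changes being related to response, which physician-chosen care permits but the Protocol does not assert.

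The sizes of about 0.1 to 0.2 SD between treatments, and about 0.7 SD for a separate switcher group, rest entirely on the assumed switching model. They also assume two treatments and one-year data on everyone enrolled. With equal two-way switching under a last-treatment or non-switcher rule there is no bias. The change is worth making because the remedy is simple, but the main correlation results are not in question.

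**What to change.** For the comparison of COM change and the mediation step, classify participants by the treatment in place at the start of the period, regardless of later changes: treatment at enrollment for established patients, and the first treatment started after enrollment for new patients, who under section 8.1 enroll before any treatment. Adjust for baseline COM and baseline peak eosinophil count as well as demographics. Keep analyses by treatment received over the year if wanted, but label them descriptive.

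An ordinary time-varying treatment term in the planned mixed model is not a substitute, because switching may depend on earlier outcomes. The treatment-change assessments also collect only symptom and quality-of-life measures (section 8.4, Appendix B).

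The cost is a change of wording and derivation; no visit, sample or aspect of care is affected. The downside is that contrasts become as first treated and are diluted by later switching. Confounding by indication, including switching before enrollment in established patients, is reduced but not removed, and the text should say so.

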Creation of DNA repository

Exploratory Objective- Subjects who consent to donate blood/saliva/ stool for this study will have their sample used to isolate and study some of the proteins, RNA, and DNA (the material contained in genes) from the blood such as the level of eosinophil attraction proteins (eotaxins) and eosinophil growth factors (such as interleukin 5). DNA will be banked at CCHMC for future studies including genome wide association analyses, candidate gene analyses and sequencing. Results will be deposited into dbGAP if required by NIH. Stool will be stored and used for studies not limited to assessment of microbiome.

Specific Aim 1: Secondary Objective (Phase 2)- In Phase 2 of this study, subjects enrolled in Phase 1 will continue to be followed and assessed at each of the following time points: 1.) annually, 2.) at the time of any change in SOC treatment and 3.) at the time of any endoscopic procedure. In scenarios 1, or 2, only PRO and QoL COMs will be completed, and in scenario 3, all COMs and histological analysis will be analyzed. All patients will be undergoing SOC during this time; SOC treatment will be the choice of the attending physician and may include systemic or topical steroids, diet, or immunosuppression. This is not an interventional study and thus *treatment will be monitored, but not prescribed* as a part of this protocol. This is a natural history study, and since SOC *maintenance* treatments and paradigms do not yet exist, we will only monitor COMs and histology over time and not dictate treatments. We have taken this approach for several reasons including the capture of “real world” data such that study findings are broadly applicable to the EoE, EG, and EC populations at large, to allow entry of the largest cohort of subjects independent of therapeutic intervention, and to better understand patient adherence to a prescribed therapeutic regimen as it relates to disease course.

Specific Aim 2: Primary Objective- We hypothesize that there will be largely unique gene profiles in each disease. We will utilize well characterized EoE, EG, and EC subjects and control subjects for gene expression analysis. We will perform genome-wide screening in the EG and EC populations since it is not clear what the gene expression profile is in these diseases. The EoE genome wide

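### The exploratory treatment comparison in section 12.5 adjusts only for imbalanced demographics and infers mediation from a change in significance, so both results can be artefacts

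*Protocol*

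**What the plan says.** Treatment is not randomised. Section 8.4 states: "SOC treatment will be the choice of the attending physician and may include systemic or topical steroids, diet, or immunosuppression". Section 4.1 says the same of Phase 2. Section 12.5 forms the groups after the fact: "The treatment that participants received over this period will be determined and used to classify participants into treatment group".

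The comparison is introduced with the words "As a supportive and exploratory analysis", and its adjustment set is its own: "the change in COMs will be compared between treatment groups while adjusting for imbalanced demographic variables". The sentence that carries the earlier covariates forward belongs to the preceding regression of change in COM on change in eosinophil count, not to this comparison.

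The mediation step follows: "Should there be significant differences among treatment groups, the change in peak eosinophil count or histological variables will be introduced into the model". The criterion is then: "Change in the significance of the coefficient for the group difference is in support of the mediator effect". No estimate of an indirect effect and no interval is called for.

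Section 8.4 also limits annual and treatment-change assessments to symptom and quality-of-life measures. Histology comes only with an endoscopy.

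**The concern.** There are two separate problems.

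**The mediation criterion.** The step is entered only after a significant group difference, so the change in significance that matters is its loss. Significance can be lost without mediation, because adding a variable correlated with treatment inflates the standard error of the treatment coefficient. It can survive real mediation when the remaining direct effect is well estimated. The criterion therefore answers a question about precision, not about the indirect effect.

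**The adjustment set.** If physicians choose treatment partly on how ill the patient is, groups differ at baseline in severity. Severe scores tend to move back towards the mean. Demographics do not capture this. The baseline COM, baseline eosinophil count, disease duration and new versus established cohort are all available, but none is named for this comparison.

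At stake is the response-to-therapy part of the secondary objective (section 3.2), and the protocol's interest in whether eosinophil counts track disease activity (section 2.1.2).

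**Working it through.** The protocol gives no effect size, power, alpha or number of groups for this step, so there is no stated figure to reproduce. The alpha of 0.01 in section 12.4 belongs to the correlation analysis. **Assumptions:** two equal groups, two-sided alpha 0.05, residual SDs of 1, and n = 150, 300 and 600 (the planned EC, EG and EoE sizes in section 12.4). Each simulated setting used 2,000 to 4,000 data sets.

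**Models.** Let T be treatment group, M the change in eosinophils and Y the change in COM.
- Model 1: Y = c + τT + error.
- Model 2: Y = c′ + τ′T + βM + error.
- Treatment shifts M by a (in SD). The indirect effect is a × β = τ − τ′. No mediation means β = 0 and τ = τ′.

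**1. No mediation.** With equal groups, adding M multiplies the standard error of the treatment coefficient by √(1 + a²/4). At 80% power the expected test statistic in Model 1 is 1.96 + 0.84 = 2.80. The last column is simulated and is nearly the same at each n.

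| a (SD) | SE factor | Expected statistic in Model 2 | Significance lost, given a significant Model 1 |
|---|---|---|---|
| 0.5 | 1.03 | 2.72 | about 5–6% |
| 1.0 | 1.12 | 2.50 | about 13–16% |
| 1.5 | 1.25 | 2.24 | about 26–29% |
| 2.0 | 1.41 | 1.98 | about 39–40% |

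A direct test of the indirect effect gave false support in about 4–7%.

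**2. Half the effect mediated, a = 1.0.**
- Total effect at 80% power: significance is lost in about 70%, so mediation is missed in about 30% at every n.
- Total effect fixed at 0.7 SD, so the direct effect is 0.35. At n = 300 the standard error is √(4/300) × 1.118 = 0.129 and the expected statistic is 0.35/0.129 = 2.71. At n = 600 it is 0.35/0.0913 = 3.83. Simulated miss rates are about 80% (n = 300) and 97–98% (n = 600).

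**3. Confounding by severity, no treatment effect.** The spurious difference in change equals the baseline gap × (1 − one-year correlation). For a 0.5 SD gap:
- correlation 0.7: 0.5 × 0.3 = 0.15 SD;
- correlation 0.4: 0.5 × 0.6 = 0.30 SD.

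Across these two correlations the false-positive rate is about 22–40% at n = 150, 39–67% at n = 300 and 66–92% at n = 600. Adding the baseline COM returns it to 4–6%.

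**4. Unequal samples.** Suppose M is unrelated to everything but known only in participants with follow-up endoscopy. At 80% power, significance is lost in about 15%, 31% and 51% when 80%, 60% and 40% have it, from the smaller sample alone. With both models fitted on the same participants the loss is about 1% or less.

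**The case against.** **Weight.** The analysis is labelled supportive and exploratory, the rule speaks only of support, and no primary endpoint or sample size depends on it. This stands and limits the importance of the point. It does not make the criterion valid.

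**Certainty.** A reader might infer that the rule usually misfires, or that its false-support and miss rates occur together at their worst. They do not. In every no-mediation setting tried at 80% power, most significant comparisons keep their significance. At 99% power false support falls to about 2%, 6% and 13% for shifts of 1.0, 1.5 and 2.0 SD. The very high miss rates need a large total effect such as 0.7 SD, where power is near 100%.

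**Direction of bias.** A reader might infer that treatment is documented as following severity. The protocol says only "SOC treatment will be the choice of the attending physician". Participants enter regardless of treatment status, and harder-to-treat disease could bias the comparison the other way. The regression-to-the-mean figures are therefore conditional. What stands is that nothing in the adjustment protects against either direction.

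**The change-on-change regressions.** A reader might extend the criticism to these because their covariate list does not name the baseline COM. The documents do not support that, because the list is expressly open: "Covariates in the model will include, but are not limited to, sex, age group, atopic disease, race, disease duration, and medication usage".

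**The remedy.** An interval for the indirect effect does not remove unmeasured common causes. With an assumed adherence factor driving both changes and no eosinophil effect on the COM, a bootstrap interval adjusted for baseline COM and eosinophils still excluded zero in 81–100% of runs. This stands, and it is why the results should be worded as associations.

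**Conclusion.** The point holds for the supportive and exploratory treatment comparison in section 12.5. A change in significance is not a valid criterion for mediation. Adjustment for imbalanced demographics alone leaves confounding by indication and regression to the mean uncontrolled. Either result can be an artefact.

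The sizes depend on the settings. False support for mediation runs from about 5% to 39% over the shifts tried, at 80% power. Real half-mediation is missed in about 30% at that power, and far more often when the total effect is large. The spurious treatment difference of 0.15 to 0.30 SD applies if treatment choice follows severity with a 0.5 SD gap. All effect sizes, the two-group layout and alpha 0.05 are assumptions.

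The primary correlation analyses and the change-on-change regressions are not affected. The wording should be corrected because the text fixes both rules and the correction is cheap.

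**What to change.** In section 12.5:

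1. Replace the significance criterion with an estimate of the indirect effect (product or difference of coefficients) and its bootstrap confidence interval.
2. Fit both models on the same participants, namely those with follow-up histology, and state how many they are.
3. Replace the imbalanced-demographics adjustment with a pre-specified set: baseline COM, baseline peak eosinophil count, disease duration, new versus established cohort, age group and sex.
4. Report the treatment and mediation results as associations, because unmeasured confounding remains.

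The cost is a few degrees of freedom and a little more analysis work. No new data are needed. Restricting to participants with follow-up histology may reduce the sample for the paired models, and they may not represent the whole cohort. The full-sample comparison can still be shown beside them.
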